5.3 Measurements of Study Variables

5.3.1 Study Process

a. Enrollment

Subjects who meet the eligibility criteria will be required to sign an informed consent form and HIPAA authorization prior to enrollment. Subjects will receive identification numbers at this time and will be considered enrolled into the study. Patient demographic characteristics, prior contraceptive method, postpartum and breastfeeding status will be recorded. All subjects will undergo a history and physical examination including pelvic examination, height and weight if this was not done within an age-appropriate interval. A baseline BMI will be calculated. A Pap test using ThinPrep[®] will be obtained if none has been taken in the preceding 12 months. A retrospective symptom diary to date of ESI insertion and prospective symptom diaries for the duration of the study will be provided to the patient with instructions to contact study personnel if materials are lost or more are needed.

b. Randomization

Patients enrolled in the study at the time of ESI insertion who either report unacceptable bleeding when contacted by study personnel at 13 weeks post-ESI insertion or self-report unacceptable bleeding after 13 weeks post ESI insertion will be offered randomization to placebo or Doxycycline. Randomization will be done with stratification based on: age (< 30 years, ≥ 30 years), postpartum status and body mass index (BMI < 30, BMI ≥ 30). The randomization will be performed using a dynamic allocation approach based on the Pocock-Simon method to ensure a balance in the treatment groups across the stratification levels. The randomization assignment for each patient will be obtained upon entering the patient's stratification levels into a web-based application created and supported by the Division of Biomedical Statistics and Informatics. Investigators and patients will be blinded to group assignment. For this reason, all pills will be made to look identical. **Enrollment of new patients will continue until approximately 100 patients are randomized (50 in each group).** Additional patients will need to be enrolled given the lower than expected reported unacceptable bleeding rates.

c. Placebo group

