interval to allow for assessment of efficacy of each course of Doxycycline. Rates of unacceptable bleeding in all patients remaining in the study at 26 weeks post-randomization will be calculated and participation in the study will end. If patients request ESI removal at any time during the study after randomly assigned treatment, study participation will be recorded as a **removal**. Method satisfaction will be assessed at removal and study participation will end. Patients will be provided with alternative contraception of choice at their expense. **Need for additional treatment at >4 weeks post-randomized treatment will represent the primary endpoint.** Satisfaction with ESI at randomization, and 13 and 26 weeks post randomization, and method continuation at 26 weeks post-randomization represent the secondary endpoints.

j. Post-treatment Followup

All patients will be contacted by study personnel at 26 weeks (\pm 2 weeks) post-randomization for final satisfaction survey and weight. Study completion BMI will be calculated. All diaries will be collected for analysis and patients will receive remuneration. When all patients complete the study, the data will be unblinded for analysis.

k. Special Considerations

If patients receive randomized treatment toward the end of the 39 week study interval (rather than at about 13 weeks post ESI insertion), post-treatment data for at least 13 weeks will be collected for a maximum study length of 52 weeks post-ESI insertion.

l. Additional testing

Additional laboratory testing or imaging for heavy or unusual bleeding will be individualized as clinically indicated.

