5.4.1 Power statements

Based on prior Mayo data, we anticipate about 30% of patients will develop unacceptable bleeding following ESI insertion.[3,29] These patients will be approached for participation in this study. The study plans to randomize a total of 100 patients with unacceptable bleeding to either placebo (N=50) or Doxycycline (N=50). The following calculations were based on a two-sided chi-square test with a type I error rate of 0.05.

Aim 1: Of the patients with bleeding concerns, based on our prior experience we anticipate that 44% of the patients randomized to Doxycycline will request additional treatment, and about 80% in the placebo arm. We are purposely overestimating the placebo effect over that noted in our cohort (92% removal requests) to allow for variation in the study group. Given the sample size of 50 per treatment arm, the study will have >90% power to detect the anticipated difference in the need for additional treatment.

Aim 2: Across the two arms, we anticipate that 66 of the 100 patients will request additional treatment and will receive additional treatment with Doxycycline. Within this subset we plan to estimate the method continuation rate following additional treatment. Based on a sample size of 66, the ½ width for a 95% CI around an estimate of 75% is ±10%.

Aim 4: Among the anticipated 66 patients who will request additional treatment for continued unacceptable bleeding at 26 weeks post-ESI insertion, we plan to quantify the patient satisfaction rate. If we assume 75% will be “very satisfied” or “satisfied”, then the ½ width for a 95% CI around this estimate will be ±10%.

5.4.2 Proposed Statistical Analysis:

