Patients will be analyzed according to their randomized treatment arm. All calculated p-values will be two-sided and p-values less than 0.05 will be considered statistically significant. Analyses will be performed using SAS software package (version 9.2). Comparisons of categorical endpoints (e.g. need for additional treatment, bleeding pattern based on the WHO classification, presence of adverse event(s), satisfaction survey questions) between the two arms will be evaluated using the chi-square test. Additional comparisons of these endpoints, adjusted for potential confounders, will be assessed by fitting separate logistic regression models. Time-to-event methodology (e.g. Kaplan-Meier method and Cox proportional hazards regression models) will be utilized for binary versions of these endpoints if patient follow-up becomes an issue and patients don't comply with the planned follow-up before completing the study. Poisson regression models will be used to compare the diary responses between the treatment arms. In the Poisson model, the endpoint will be the number of bleeding and spotting days per patient (and likewise the number of days with additional symptoms), offset by the total days of diary follow-up per patient. Ninety-five percent confidence intervals (95% CI) will be constructed around the estimates for method continuation and satisfaction.

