7.1 Study Duration

Patients will be offered enrollment in the study upon ESI insertion. They will begin completing weekly prospective symptom diaries at that time. If they report unacceptable bleeding at the time of study personnel contact at 13 weeks post ESI insertion or self-report unacceptable bleeding at > 13 weeks post ESI insertion, they will be offered randomization to Doxycycline or placebo. They will continue prospective weekly symptom diaries for 26 weeks post randomization or until they discontinue study participation. A patient who self-reports unacceptable bleeding late in the study interval will be followed for at least 13 weeks after randomized treatment in order to have a meaningful study conclusion. The maximum study length for such a patient would be 52 weeks from ESI insertion. Based on current numbers of ESI insertions per year, **we anticipated that all 100 subjects with unacceptable bleeding will randomized within 30 months. However, the rate of reported unacceptable bleeding was lower than expected and therefore we propose an additional enrollment of 120 patients (total 470 patients) to achieve 100 randomized patients.**

8.0 Study Expectations and Limitations:

This study is a double blinded placebo-controlled randomized prospective trial of Doxycycline for the management of ESI-related unacceptable bleeding. The study will include US women regardless of BMI. Randomization will be done using a dynamic

allocation process with stratification by age, BMI and postpartum status. This will avoid confounding effects of these variables on our outcomes.

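### The primary chi-square leaves out the three minimization factors, and section 5.4.2 specifies no effect estimate with a 95% CI for the primary endpoint

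*Combined protocol and SAP*

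**What the plan says.** - **Allocation (5.3.1 b, Randomization).** Assignment is made "using a dynamic allocation approach based on the Pocock-Simon method", balancing age (under 30 or not), postpartum status and BMI (under 30 or not). Section 8.0 gives the reason: "This will avoid confounding effects of these variables on our outcomes".
- **Primary endpoint (5.3.1 i).** "Need for additional treatment at >4 weeks post-randomized treatment will represent the primary endpoint".
- **Sample size (5.4.1).** "The following calculations were based on a two-sided chi-square test with a type I error rate of 0.05". There are 50 women per arm, and for the rates "we anticipate that 44% of the patients randomized to Doxycycline will request additional treatment, and about 80% in the placebo arm".
- **Analysis (5.4.2).** Categorical endpoints "between the two arms will be evaluated using the chi-square test", with need for additional treatment the first example given. Then: "Additional comparisons of these endpoints, adjusted for potential confounders, will be assessed by fitting separate logistic regression models". The significance rule is "All calculated p-values will be two-sided and p-values less than 0.05 will be considered statistically significant".
- **Intervals (5.4.2).** 95% confidence intervals are planned for the method continuation and satisfaction estimates. None is mentioned for the between-arm difference in the primary endpoint.

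**The concern.** There are three linked gaps.

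1. **Analysis and allocation do not match.** Minimization removes most chance imbalance between arms on the three factors. The chi-square variance still allows for that imbalance. If the factors predict outcome, the variance is too large and the test rejects less often than 5% under the null. The plan balances on these variables because it sees them as possible sources of confounding, but does not carry them into the main test.
2. **The adjusted analysis is open.** No covariates or selection rule are given, and the adjusted models stand only as additional comparisons. Section 5.3.1 a collects demographics, prior contraceptive method, postpartum and breastfeeding status, and BMI, so several adjusted results are possible and nothing says which one counts.
3. **No estimate is specified for the primary endpoint.** As written, the primary result is a p-value. After a non-significant result, readers would have no planned interval showing which effects are excluded.

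Gaps 2 and 3 can be checked by reading. The size of gap 1 has to be calculated under assumptions.

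**Working it through.** **Inputs from the documents:** 50 per arm; 44% vs 80%; two-sided alpha 0.05; three two-level allocation factors.

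**Assumptions not in the documents:** prevalences of the three factors (40/20/35% or 40/35/30%), a common odds ratio (OR) per factor, and the probability of assigning the balancing arm (0.8 or 1.0).

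**Step 1. Reproduce the stated power.**
- Pooled rate: (0.44 + 0.80)/2 = 0.62.
- Null SE: sqrt(2 × 0.62 × 0.38/50) = 0.0971.
- Alternative SE: sqrt((0.44 × 0.56 + 0.80 × 0.20)/50) = 0.0902.
- z = (0.36 − 1.96 × 0.0971)/0.0902 = 1.88, so power is 97.0%.

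Exact enumeration also gives 97.0%, or 95.2% with continuity correction. The plan's figure of more than 90% holds.

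**Step 2. Size of the chi-square under minimization.** Simulated trials of 100 women, prevalences 40/20/35%, 62% event rate in both arms, 6,000 trials per cell (Monte Carlo SE about 0.3 points). The adjusted test is the likelihood-ratio test from a logistic model with the three factors.

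| OR per factor | Chi-square, prob. 1.0 | Chi-square, prob. 0.8 | Adjusted, prob. 1.0 |
|---|---|---|---|
| 1 | 5.2% | 5.0% | 5.6% |
| 1.5 | 5.3% | 5.0% | 6.1% |
| 2 | 4.6% | 4.8% | 5.8% |
| 3 | 3.9% | 3.8% | 5.6% |
| 5 | 2.6% | 3.1% | 5.6% |

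With prevalences 40/35/30% and probability 0.8, separate runs gave 4.6 to 4.8% at OR 2 and 3.3 to 4.3% at OR 3. With weak or null factors the chi-square holds its level. Conservatism appears at about OR 2 and becomes clear at OR 3.

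**Step 3. Power, chi-square vs adjusted.** The 80% rows use prevalences 40/20/35% and probability 1.0 (3,000 trials per cell). The 70% row uses 40/35/30% and 0.8 (4,000 trials per cell).

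| Rates | OR 2 | OR 3 |
|---|---|---|
| 80% vs 44% (planned) | 97.2% vs 97.7% | 98.0% vs 98.8% |
| 80% vs 55% (assumed) | 78% vs 81% | 78% vs 83% |
| 70% vs 44% (assumed) | 78.0% vs 80.1% | 78.8% vs 83.0% |

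At the planned effect the difference is under 1 point in these cells. At the smaller effects it is about 2 to 5 points. Some of that is not real gain, because the adjusted test rejects slightly more than 5% under the null (Step 2).

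**Step 4. The interval the plan does not specify.** At planning rates the unadjusted half-width is 1.96 × 0.0902 = 0.177. A difference of 36 points would have a 95% CI of about 18 to 54 points.

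**The case against.** The strongest reply is that a prespecified unadjusted chi-square is a legitimate primary test and is the one used for the power calculation. Any error is on the safe side, so false positives are not inflated. The planned effect leaves ample power. Adjusted logistic models are already planned and would ordinarily yield an odds ratio with an interval, and a risk-difference interval can be computed from the two observed proportions.

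All of that stands, and it rules out several stronger readings that a reader might infer:

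- **That the primary test runs below 5%, as a fact.** This needs the factors to be prognostic. Section 8.0 gives a reason for balancing on them, not evidence that they predict outcome.
- **That the power statement is wrong.** It reproduces at about 97%.
- **That covariates will be chosen after seeing the data.** The text leaves them unnamed; it does not describe data-driven selection.
- **That adjustment is absent.** It is planned, but as an additional analysis.

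What the reply does not answer is that the allocation factors appear nowhere in 5.4.2, that nothing fixes which adjusted model counts, and that an interval which could be computed is not the same as one specified in advance. The smaller-effect case is also not remote. The 44% and 92% behind the planning rates are removal requests in a retrospective cohort (1.0, 4.0), whereas the trial endpoint is need for additional treatment. Section 4.0 also cites a follow-up study of a shorter course with no improvement over placebo.

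**Conclusion.** The point holds as an improvement to a valid analysis. Two parts need no assumption: the covariates of the adjusted model are unnamed, and no effect estimate with a 95% CI is specified for the primary endpoint. The third, leaving the minimization factors out of the primary test, has a modest and conditional cost. If each factor carries an odds ratio of about 2 to 3, size falls to about 4 to 5%. Power is then roughly 2 to 5 points lower at a smaller effect such as 70% vs 44%, partly because the likelihood-ratio comparator runs slightly above 5%, and about 1 point lower at the planned effect. If the factors are weak (odds ratio 1 to 1.5), size stays near 5%. The documents do not say which case applies.

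**What to change.** In section 5.4.2:

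1. Make the primary analysis a logistic model for need for additional treatment, with arm plus age, postpartum status and BMI (age and BMI may enter as continuous values). Report the standardized risk difference with its 95% CI.
2. Keep the unadjusted chi-square as a sensitivity analysis.
3. Replace the open reference to confounders with this fixed three-factor list.
4. State how the p-value and interval are obtained. Because the likelihood-ratio test can run slightly above 5% with 100 women, consider a score test, or base inference on the standardized estimate with a robust or bootstrap interval.

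The cost is analysis-plan wording. The three factors are already entered to obtain each assignment, so no new data, visits or sample size are needed. The one small downside is the slight excess over 5% that item 4 addresses.

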5.2.1 Patient selection

After appropriate IRB approval, ESI users aged 18-51 years old who meet the inclusion and exclusion criteria, and sign a written consent will be **enrolled in the study at the time of ESI insertion**. Every effort will be made to insert ESI on the same day as consent unless medically contraindicated. They will complete a prospective symptom diary from date of ESI insertion. All patients will be contacted by study personnel 13 weeks after enrollment and queried as to the presence of unacceptable bleeding. Bleeding concerns will be objectively assessed using a modification of the Pictorial Blood Loss Assessment Chart (PBLAC) [27]. Patient-initiated contact in with bleeding concerns at any time after 13 weeks post ESI insertion will result in enrollment and randomization at the time of contact. **The basis for randomized treatment will be whether or not the bleeding is “unacceptable” to the patient. This is inherently subjective, but constitutes the basis for most removal requests.** Patients who report unacceptable bleeding at 13 weeks post-ESI insertion, and those who call with bleeding concerns after 13 weeks post ESI insertion, will be randomized into two groups (Doxycycline or placebo). Patients who do not report unacceptable bleeding will continue to complete diaries and may be eligible for randomized treatment if unacceptable bleeding develops. Patients will receive diaries sufficient for completion of the study with instructions to contact study personnel if more diaries are needed or if diaries are lost. Patients and investigators will be blinded to the group assignment as well as the study coordinator who will be responsible dispensing of appropriate study medication by the pharmacy.

Patients who continue to have unacceptable bleeding after 4 weeks post-randomized treatment and wish to have secondary treatment will be treated with Doxycycline. Secondary treatment will not be blinded. Rates of unacceptable bleeding and patient satisfaction scores at 26 weeks post-randomized treatment in remaining study participants will be calculated.

[figure not shown]

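### Section 5.4.2 compares diary day counts by Poisson regression with no dispersion handling; unless women differ by very few bleeding days, the p-values will be too small

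*Combined protocol and SAP*

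**What the plan says.** Section 5.4.2 assigns Poisson regression to the diary responses. "In the Poisson model, the endpoint will be the number of bleeding and spotting days per patient", and the same model serves a second endpoint: "and likewise the number of days with additional symptoms), offset by the total days of diary follow-up per patient". The significance rule covers these tests with all others: "All calculated p-values will be two-sided and p-values less than 0.05 will be considered statistically significant".

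The section specifies the model family, the endpoints and the offset. Neither it nor any other section mentions overdispersion, a scale parameter, a robust variance, a negative binomial model or a check of model fit.

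Three other places bear on the point:

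- **Entry.** Section 5.2.1 makes entry to randomized treatment depend on whether the woman finds her bleeding unacceptable: "This is inherently subjective, but constitutes the basis for most removal requests". No number of bleeding days is required.
- **Expected outcome.** Section 5.4.1 expects a mixed result within each arm: "we anticipate that 44% of the patients randomized to Doxycycline will request additional treatment, and about 80% in the placebo arm".
- **Follow-up.** Section 7.1 sets diaries at 26 weeks after randomization or until the woman stops. Late-randomized women "will be followed for at least 13 weeks after randomized treatment in order to have a meaningful study conclusion", and section 5.3.1(k) caps the total: "post-treatment data for at least 13 weeks will be collected for a maximum study length of 52 weeks post-ESI insertion". Section 8.3 accepts that women may leave or have the implant removed at any time. Diary length will therefore differ between women.

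**The concern.** A Poisson model with no further option derives its standard errors from the assumption that the variance equals the mean. The offset corrects for length of follow-up, not for dispersion. If counts vary more than the assumption allows, standard errors are too small and the 0.05 rule no longer holds 5%.

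Clustering of bleeding days into episodes does not settle the direction. In identical women, very regular episodes or independent days make the test conservative, while irregular episodes make it anti-conservative. The direction rests mainly on how much women differ from one another. The subjective entry rule and the expected mix of women with and without continued need for treatment make such differences likely. For symptom days the documents describe no episode structure, so the concern there rests on differences between women alone.

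At stake is a chance difference in bleeding or symptom days being reported as a drug effect. The expected findings in section 8.4 do not rest on day counts.

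**Working it through.** **The plan's own figure.** No mean, SD, dispersion or power is given for the day counts. The only stated power is above 90% for the primary endpoint (44% against 80%, 50 per arm, two-sided chi-square at 0.05). It reproduces at 97.0% and does not involve the Poisson model.

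**Inputs.** From the plan: 50 per arm, two-sided 0.05, a 13-week reference period (13 × 7 = 91 days), and 44% and 80% needing additional treatment. Assumed: a pattern of 5 days on and 15 off, so the mean is 91 × 5/20 = 22.75 days. All spreads are also assumed.

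**1. False-positive rate by dispersion.** Let phi be variance divided by mean of the per-woman counts. The plain Poisson standard error is too small by a factor sqrt(phi), so the true level is 2 × (1 − Φ(1.96/sqrt(phi))). Simulation used beta-binomial counts over 91 days, no treatment effect and 20,000 trials:

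| phi | Plain Poisson | Sandwich |
|---|---|---|
| 1.6 | 12.0% | 5.5% |
| 3.2 | 27.0% | 5.4% |
| 4.8 | 37.3% | 5.5% |
| 7.5 | 47.9% | 5.2% |
| 13.3 | 58.8% | 5.1% |

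The formula agrees: at phi = 1.6, 1.96/1.265 = 1.55, which gives 12%.

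**2. Break-even.** Within one woman, independent days give phi = 1 − 0.25 = 0.75. The most regular episodes simulated gave 0.48. The between-woman SD that brings phi up to 1 is sqrt((1 − phi_within) × mean):

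- Independent days: sqrt(0.25 × 22.75) = 2.4 days.
- Most regular episodes: sqrt(0.52 × 22.75) = 3.4 days.

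With independent days, the break-even SD is 1.0, 2.1, 3.1 and 4.7 days at means of 10, 20, 30 and 45.

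**3. The mix in section 5.4.1.** If a share q still needs treatment and has more bleeding days by some gap, the between-woman SD is gap × sqrt(q(1 − q)). This factor is 0.496 at q = 0.44 and 0.40 at q = 0.80. The break-even gap is therefore 2.4/0.496 = 4.8 to 2.4/0.40 = 6.0 days, or 6.9 to 8.6 days with the most regular episodes. Null false-positive rates at q = 0.44, 0.62 (the midpoint) and 0.80:

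| Gap (days) | Independent days | Regular episodes |
|---|---|---|
| 0 | 2.4 / 2.4 / 2.3% | 0.3 / 0.3 / 0.4% |
| 10 | 14.3 / 14.0 / 10.3% | 11.0 / 12.7 / 6.6% |
| 15 | 27.1 / 26.9 / 20.0% | 25.1 / 24.5 / 17.9% |
| 20 | 37.9 / 37.2 / 29.9% | 37.0 / 34.7 / 28.1% |

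The sandwich gave 4.4% to 6.1% throughout.

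**4. Identical women.** Making episodes progressively more regular moved phi through 4.69, 2.12, 1.21, 0.76 and 0.48, with plain Poisson rejecting 36.7%, 18.4%, 7.2%, 2.2% and 0.5%. Episode structure alone can push the level either way.

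**5. Symptom days.** Assumed mean/SD of the count (phi = SD²/mean): 5/3 (1.8), 13.9%; 10/5 (2.5), 21.4%; 5/5 (5), 37.8%; 10/10 (10), 53.7%. The sandwich gave 5.5% to 6.4%.

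**6. Unequal follow-up.** Where women differ, variance grows faster than in proportion to the mean as diaries lengthen. A single Pearson scale does not capture that. Using the five spreads from step 1 and assumed shares:

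| Diary days (shares) | Plain Poisson | Pearson scale | Sandwich |
|---|---|---|---|
| 91/182 (50:50) | 19–67% | 5.6–6.1% | 5.5–5.7% |
| 30/91/182 (25:25:50) | 19–68% | 7.0–8.3% | 5.6–5.9% |
| 14/182 (40:60) | 21–70% | 8.7–11.0% | 5.8–6.0% |

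**The case against.** The strongest reply is that this is unstated detail rather than an error. Section 5.4.2 names no variance estimator for its logistic or Cox models either, does not forbid a scale or robust option, and a competent analyst might add one. That is fair as far as it goes. But the plan commits to this model and this threshold, and the commitment as written does not hold 5% under modest variation.

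Second, every spread used above is assumed. The 44% and 80% refer to requests for treatment, which rest on the same subjective judgement as entry, and no section gives a gap in days between women who ask and women who do not. Open-label doxycycline after a request could also change any gap, and the mix calculation does not model this. These points stand. They limit what can be said about size, not the conditional result, and the break-even is low.

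Third, the preference for the sandwich over a Pearson scale can be pressed too far. The 11.0% figure needs 40% of women to have only 14 diary days, a share found nowhere in the documents. With 5% to 20% of women at 30 days and the rest at 91 or a 91/182 split, the Pearson scale gave 5.5% to 6.9% against 5.3% to 5.8%. With equal follow-up the two hardly differ. Any stated dispersion handling would remove most of the problem; the sandwich is simply the safer choice when diary lengths differ.

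Finally, the rate-ratio estimate itself is unaffected.

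**Conclusion.** The concern holds in conditional form. The plan names no dispersion handling, and its Poisson p-values for bleeding and symptom days are too small once phi exceeds 1. At the assumed mean of 22.75 days in 91, that happens at a between-woman SD of 2.4 to 3.4 days. A separate null simulation with independent days within each woman and between-woman SDs of 3, 5, 8, 12 and 16 days gave 6.5%, 15.1%, 29.7%, 46.4% and 56.7% for plain Poisson, against 5.2% to 5.8% for the sandwich. The true dispersion cannot be fixed from the documents, and nearly identical women would make the test conservative.

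The scope is limited to the day-count comparisons. The primary endpoint as defined in section 5.3.1(i), its chi-square test and power, and the comparison of WHO bleeding patterns are untouched. One qualification: section 5.3.2 item A also mentions the diary under the primary endpoint, so the secondary status of the day counts is not stated with full consistency. The change should be made but does not threaten the main conclusion.

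**What to change.** Before unblinding, add one sentence to section 5.4.2: the Poisson models for bleeding and spotting days and for symptom days, with log diary days as offset, will use a robust (sandwich) variance for tests and confidence intervals. This is valid whether counts are over- or under-dispersed. If the slight excess over 5% matters, a leverage-corrected sandwich with a t reference on 50 + 50 − 2 = 98 degrees of freedom gave 4.7% to 5.0% under the unequal follow-up in step 6.

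The cost is that sentence and one model option; data collection, sample size and the primary analysis do not change. The price is usually wider standard errors, by sqrt(1.6) ≈ 1.3 to sqrt(13.3) ≈ 3.6 times over the dispersions examined, and so fewer nominally significant day-count results. If days were independent in identical women, standard errors would instead be narrower, by about sqrt(0.75) ≈ 0.87.
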